4.7 Data Quality

Monitoring and auditing procedures defined/agreed by the sponsor will be followed, in order to comply with GCP guidelines. Each center will be visited by a monitor to ensure compliance with the study protocol, GCP and legal aspects. This will include on-site checking of the specific data recorded in the case report forms (CRF) for completeness and clarity, cross-checking with source documents, and clarification of administrative matters, and review of the clinical supplies.

4.8 Documentation

Entries made in the CRF must be either verifiable against source documents, or have been directly entered into the CRF, in which case the entry in the CRF will be considered as the source data. The source data parameter to be verified and the identification of the source document must be documented. The study file and all source data should be retained until notification given by the sponsor for destruction.

^{jjjj}: This bullet for survival status was added in Amendment 3. See Section 10.3, Modification 1.

^{kkkk}: The text regarding assessment of survival in the follow-up period was added in Amendment 3. See Section 10.3, Modification 1.

^{llll}: This bullet for survival limiting was added in Amendment 7. See Section 10.5.5 Modification 5.

^{mmmm}: Section 4.6.4, Drug Concentration Measurements, was deleted in Amendment 3. See Section 10.3, Modification 6.

4.9 End of Study

According to Directive EU 2001/20/EC the end of the trial will be notified to the competent authorities of the member states concerned based on the following definition. For the member states involved, the end of trial will be reached when the last visit of the last patient for all centers in the territory of this member state has occurred. This can be reached based on the last patient stopping study medication or being switched to any other form of study drug supply. In the event that any other mechanism of drug supply is established, the present study will end when all patients have transitioned or discontinued from this study for another reason (e.g. consent withdrawal, lost to follow-up, death, sponsor decision). Until the transition, patients will continue to follow all the procedures and visits required in the current version of the protocol.ⁿⁿⁿⁿ As soon as the end of trial according to this definition has been reached in all participating centers within and outside the community has occurred, the complete end of trial will be reached.

5. Ethical and legal aspects

5.1 Ethics Committee (EC) or Institutional Review Board (IRB)

Documented approval from appropriate Ethics Committee(s)/IRBs will be obtained for all participating centers/countries prior to study start, according to GCP, local laws, regulations and organizations. When necessary, an extension, amendment or renewal of the Ethics Committee approval must be obtained and also forwarded to the Sponsor. The Ethics Committees^{oooo} must supply to the Sponsor, upon request, a list of the Ethics Committee members involved in the vote and a statement to confirm that the Ethics Committee is organized and operates according to GCP and applicable laws and regulations.

ⁿⁿⁿⁿ Added clarification on the definition of the end of study with Amendment 8. See Section 10.6.7, Modification 7.
^{oooo}: Additional text was added in Amendment 3 to include the head of the center for sites in Japan. See Section 10.3, Modification 3. Text to include the head of the center for study sites in Japan removed with Amendment 8. See Section 10.6.8, Modification 8.

5.2 Ethical Conduct of the Study

The procedures set out in this protocol, pertaining to the conduct, evaluation, and documentation of this study, are designed to ensure that the Sponsor and Investigator abide by Good Clinical Practice Guidelines and under the guiding principles detailed in the Declaration of Helsinki. The study will also be carried out in keeping with applicable local law(s) and regulation(s). This may include an inspection by the Sponsor representatives and/or Regulatory Authority representatives at any time. The Investigator must agree to the inspection of study-related records by the Regulatory Authority/Sponsor representatives, and must allow direct access to source documents to the Regulatory Authority/Sponsor representatives.

The study site will be monitored by Bayer Representatives to verify the timely and accurate reporting of treatment related Serious Adverse Events, dispensing of Clinical Supplies to appropriate patients and accurate maintenance of CRF as well as Study and Regulatory Documents.

Modifications to the study protocol will not be implemented by either the Sponsor or the Investigator without agreement by both parties. However, the Investigator may implement a deviation from, or a change of, the protocol to eliminate an immediate hazard(s) to the trial subjects without prior EC/IRB/Sponsor approval/favorable opinion. As soon as possible, the implemented deviation or change, the reasons for it and if appropriate the proposed protocol amendment should be submitted to the EC/IRB/Sponsor. Any deviations from the protocol must be fully explained and documented by the Investigator.

Regulatory Authority Approvals/Authorizations

Regulatory Authority approvals/authorizations/notifications, where required, must be in place and fully documented prior to study start.

5.3 Subject Information and Consent

A core information and Informed Consent Form will be provided. Prior to the beginning of the study, the Investigator must have the ECs/IRB written approval/favorable opinion of the written Informed Consent Form and any other written information to be provided to subjects. The written approval of the EC/IRB together with the approved subject information/Informed Consent Forms must be filed in the study files.

Written informed consent must be obtained before any study specific procedure takes place in this program. To ensure continuing administration of medication, patients will be consented and registered for this program while still participating in their original trial (see Section 4.6.3).

Participation in the study and date of informed consent given by the subject should be documented appropriately in the subject's files.

5.4 Insurance

All subjects participating in the study will have insurance coverage by the Sponsor, which is in line with applicable laws and/or regulations.

5.5 Confidentiality

All records identifying the subject will be kept confidential and, to the extent permitted by the applicable laws and/or regulations, will not be made publicly available.

Subject names will not be supplied to the Sponsor. Only the subject number will be recorded on any study related documents or forms, and if the subject name appears on any other document (eg, pathologist report), it must be obliterated before a copy of the document is supplied to the Sponsor. Study findings stored on a computer will be stored in accordance with local data protection laws. The subjects will be informed in writing that representatives of the Sponsor, EC/IRB, or Regulatory Authorities may inspect their medical records to verify the information collected, and that all personal information made available for inspection will be handled in strictest confidence and in accordance with local data protection laws.

If the results of the study are published, the subject's identity will remain confidential.

The Investigator will maintain a list to enable subjects' records to be identified.

6. Statistical methods and determination of sample size

6.1 Statistical and Analytical Plans- amended

After the end of the study^{pppp}, *descriptive analyses*^{qqqq} of demography, adverse events (including serious), laboratory data, and reasons for termination of treatment^{rrrr ssss} will be provided in the form of a written report.^{tttt uuuu}

6.2 Determination of Sample Size

Not applicable

7. Adverse events

7.1 Warnings/Precautions

As outlined in the Investigator Brochure and Safety Sections of the Product Labeling.

7.2 Adverse Event Monitoring

Subjects must be carefully monitored for adverse events. This monitoring also includes specified clinical laboratory tests. Adverse events should be assessed in terms of their seriousness, severity

pppp: The timepoint was corrected with Amendment 8. See Section 10.6.9, Modification 9.

qqqq: Text regarding the presentation of data was modified under Amendment 3. See Section 10.3, Modification 6.

rrrr: Duration of treatment and overall survival were added in Amendment 3. See Section 10.3, Modification 1 and Modification 6.

ssss: Statistical and Analytical Plans were modified by Amendment 7 to remove overall survival (OS). See Section 10.5.2, Modification 2.

tttt: Date of enrollment will be used for cases in which the originating trial was not randomized.

uuuu: Information regarding the analysis of survival data was added in Amendment 3. See Section 10.3, Modification 1.

and relationship to study medication. *Adequate medical care will be provided to the subjects for any adverse events, and the events will be followed up until resolution or stabilization.*^{vvvv}

7.3 Adverse Event Definitions

7.3.1 Adverse Event

An adverse event is any untoward medical occurrence in a subject or clinical investigation subject administered with a pharmaceutical product. The adverse event does not necessarily have to have a causal relationship with this treatment. An adverse event can therefore be any unfavorable and unintended sign (including an abnormal laboratory finding), symptom, or disease temporally associated with the use of an investigational product, whether or not considered related to the medicinal product.

Adverse events associated with the use of a drug in humans, whether or not considered drug related, include the following:

- An adverse event occurring in the course of the use of a drug product in professional practice.
- An adverse event occurring from an overdose whether accidental or intentional.
- An adverse event occurring from drug abuse.
- An adverse event occurring from drug withdrawal.
- An adverse event where there is a reasonable possibility that the event occurred purely as a result of the subject's participation in the study (eg, adverse event or serious adverse event due to discontinuation of anti-hypertensive drugs during wash-out phase) must also be reported as an adverse event even if it is not related to the investigational product.

vvvv: Sentence regarding the follow-up of adverse events was added in Amendment 3. See Section 10.3, Modification 4.

The clinical manifestation of any failure of expected pharmacological action is not recorded as an adverse event if it is already reflected as a data point captured in the CRF. If, however, the event fulfills any of the criteria for a “serious” adverse event, it must be recorded and reported as such.

If progressive disease leads to signs and symptoms that meet the “serious” criteria (ie, hospitalization, disability, death or an important medical event), the signs and symptoms should be reported as an SAE and not the underlying cause (ie, progressive disease).

7.3.2 Serious Adverse Event

A serious adverse event is any untoward medical occurrence that at any dose:

- Results in death.
- Is life-threatening.
- Requires in-patient hospitalization or prolongation of existing hospitalization.
- Results in persistent or significant disability or incapacity.
- Is a congenital anomaly or birth defect.
- Is an important medical event.

Life-threatening: The term “life-threatening” in the definition of “serious” refers to an adverse event in which the patient was at risk of death at the time of the event. It does not refer to an adverse event which hypothetically might have caused death if it were more severe

Hospitalization: Any adverse event leading to hospitalization or prolongation of hospitalization will be considered as Serious, UNLESS at least one of the following exceptions is met:

- The admission results in a hospital stay of less than 12 hours ^{www}

OR

www: The exception regarding Japan was added in Amendment 3. See Section 10.3, Modification 4. The exception regarding Japan was removed with Amendment 8. See Section 10.6.8, Modification 8.

- The admission is pre-planned (ie, elective or scheduled surgery arranged prior to the start of the study).

OR

- The admission is not associated with an adverse event (eg, social hospitalization for purposes of respite care).

However, it should be noted that invasive treatment during any hospitalization may fulfil the criteria of ‘medically important’ and as such may be reportable as a serious adverse event dependant on clinical judgement. In addition where local Regulatory authorities specifically require a more stringent definition, the local regulation takes precedent

Disability means a substantial disruption of a person’s ability to conduct normal life’s functions.

Important medical event: Any adverse event may be considered serious because it may jeopardize the subject and may require intervention to prevent another serious condition. As guidance for determination of important medical events refer to the “WHO Adverse Reaction Terminology – Critical Terms List”. These terms either refer to or might be indicative of a serious disease state.

Such reported events warrant special attention because of their possible association with a serious disease state and may lead to more decisive action than reports on other terms.

7.3.3 Unexpected Adverse Event

An unexpected adverse event is any adverse drug event, the specificity or severity of which is not consistent with the current Investigator Brochure (or Package Insert for marketed products).

Also, reports which add significant information on specificity or severity of a known, already documented adverse event constitute unexpected adverse events. *The expectedness of AEs will*

be determined by the Sponsor according to the applicable reference document and according to all local regulations.^{xxxx}

7.3.4 Relationship of Adverse Event to Investigational Product

The assessment of the relationship of an adverse event to the administration of study drug is a clinical decision based on all available information at the time of the completion of the case report form.

An assessment of ‘No’ would include:

- The existence of a clear alternative explanation, eg, mechanical bleeding at surgical site.

OR

- Non-Plausibility, eg, the subject is struck by an automobile when there is no indication that the drug caused disorientation that may have caused the event; cancer developing a few days after the first drug administration.

An assessment of ‘Yes’ indicates that there is a reasonable suspicion that the adverse event is associated with the use of the investigational drug.

xxxx: The sentence regarding expectedness of AEs was added in Amendment 3. See Section 10.3, Modification 4.

Factors to be considered in assessing the relationship of the adverse event to study drug include:

- The temporal sequence from drug administration: The event should occur after the drug is given. The length of time from drug exposure to event should be evaluated in the clinical context of the event.
- Recovery on discontinuation (de-challenge), recurrence on reintroduction (re-challenge): Subject's response after drug discontinuation (de-challenge) or subjects response after drug re-introduction (re-challenge) should be considered in the view of the usual clinical course of the event in question.
- Underlying, concomitant, intercurrent diseases: Each report should be evaluated in the context of the natural history and course of the disease being treated and any other disease the subject may have.
- Concomitant medication or treatment: The other drugs the subject is taking or the treatment the subject receives should be examined to determine whether any of them may be suspected to cause the event in question.
- Known response pattern for this class of drug:
- The pharmacology and pharmacokinetics of the test drug: The pharmacokinetic properties (absorption, distribution, metabolism and excretion) of the test drug(s), coupled with the individual subject's pharmacodynamics should be considered.

7.3.5 Severity of the Serious Adverse Event

The following classification should be used:

The intensity or severity of serious adverse events should be documented using the National Cancer Institute-Common Terminology Criteria, Version 3.0 (NCI-CTC v. 3.0).

Treatment related Serious adverse events (SAEs), as assessed by the investigator, including laboratory test abnormalities fulfilling the definition of serious, after signing the informed consent

and during follow-up period must immediately (within 24 hours of the investigator's awareness) be reported to the person detailed in the study file. A serious adverse event Form must also be completed within 24 hours of the investigator awareness and forwarded to the designated person as detailed in the study file. Each serious adverse event must be followed up until resolution or stabilization by submission of updated reports to the designated person.

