dd Laboratory evaluations have been adjusted by Amendment 7 to ensure these are not missed. See Section 10.5.4, Modification 4.

ee: Survival and ECOG performance status were added to the Case Report Form as of Amendment 3. See Section 10.3 Modification 1 and Modification 2.

medications must be recorded in the patient's source documents and may be requested at the discretion of the Sponsor.

Following the End of Treatment assessments from the original study, the following information will be recorded in the long term extension CRF: demography, date of first dose of sorafenib (Nexavar) in originating study^{ff} date of first dose of capecitabine if the patient is transferred from RESILIENCE (Study 12444),^{gg} originating study number, *ECOG performance status and survival status (dead or alive and date of death or date of last contact)*^{hh} and ongoing adverse events.

In the event the patient experiences a treatment related Serious Adverse Event, based on the definition outlined in Section 7 of this document, this event must be reported to Bayer Global Drug Safety immediately (within 24 hours of awareness) using the forms provided, and recorded in the CRF.

In the event that another mechanism of continued drug supply is established, the present study will end when all patients have transitioned to any new drug supply program or discontinued from this study for another reason (e.g. consent withdrawal, lost to follow-up, death, sponsor decision). Until the transition, patients will continue to follow all the procedures and visits required in the current version of the protocol.ⁱⁱ

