7.4 Reporting of Serious Adverse Events/Pregnancy

Serious adverse events (SAEs), including laboratory test abnormalities fulfilling the definition of serious, after signing the informed consent and during the follow-up period must immediately (within 24 hours of the investigator's awareness) be reported to the person detailed in the study file. A serious adverse event form must also be completed within 24 hours of the investigator's awareness and forwarded to the designated person as detailed in the study file. Each serious adverse event must be followed up until resolution or stabilization by submission of updated reports to the designated person. An isolated laboratory abnormality that is assigned Grade 4, according to CTC definition, is not reportable as an SAE, unless the investigator assesses that the

yyy: Language specific to the recording of adverse event information in Japan was added under Amendment 3. See Section 10.3, Modification 2. Language specific to the recording of adverse event information in Japan was removed under Amendment 8. See Section 10.6.8, Modification 8.

event meets standard ICH criteria for an SAE. CTC Grade 4 baseline laboratory abnormalities that are part of the disease profile should not be reported as an SAE, specifically when they are allowed or not excluded by the protocol inclusion/exclusion criteria. If an investigator is in doubt about the applicable reporting obligations, he/she should consult with the study monitor for the Sponsor.

CTC Grade 4 lab abnormalities will be documented in the lab data and will be reviewed on a regular basis.

When required, and according to local law and regulations, serious adverse events must be reported to the Ethics Committee and Regulatory Authorities.

Pregnancy occurring during a clinical investigation, although not considered a serious adverse event, must be reported to Bayer within the same timelines as a serious adverse event on a Pregnancy Monitoring Form. The outcome of a pregnancy should be followed up carefully and any abnormal outcome of the mother or the child should be reported. This also applies to pregnancies following the administration of the investigational product to the father prior to sexual intercourse.

8. Use of data and publication

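### Protocol 4.1 and 7.3.5 attach the 24-hour SAE report to treatment-related SAEs, 7.4 requires it for all SAEs, and no text says which scope governs

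*Protocol*

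**What the plan says.** All of the following stands in the current body of the protocol, not in the amendment history.

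- **4.1 (Study Design and Plan)** opens its reporting rule with "In the event the patient experiences a treatment related Serious Adverse Event, based on the definition outlined in Section 7" and requires such an event to reach the sponsor's drug safety group within 24 hours of awareness.
- **7.3.5 (Severity of the Serious Adverse Event)** gives a 24-hour report and a 24-hour SAE form for "Treatment related Serious adverse events (SAEs), as assessed by the investigator, including laboratory test abnormalities fulfilling the definition of serious". Its last sentence is wider: "Each serious adverse event must be followed up until resolution or stabilization by submission of updated reports to the designated person".
- **7.4 (Reporting of Serious Adverse Events/Pregnancy)** gives the same two 24-hour duties for "Serious adverse events (SAEs), including laboratory test abnormalities fulfilling the definition of serious, after signing the informed consent", with no reference to relationship. It adds: "If an investigator is in doubt about the applicable reporting obligations, he/she should consult with the study monitor for the Sponsor".
- **7.3.1 (Adverse Event)** calls for events meeting a seriousness criterion to be reported as serious, including serious signs and symptoms of progressive disease. It has no relatedness qualifier and no time limit.
- **5.2 (Ethical Conduct of the Study)** says that sponsor representatives will "verify the timely and accurate reporting of treatment related Serious Adverse Events".
- **4.7 (Data Quality)** has monitors ensure compliance with the protocol as a whole and check CRF entries against source documents.
- **4.6.2 and 4.6.3** require every SAE in the CRF, whatever its attribution.
- **4.3 and 4.6.3** require an SAE form for deaths up to 30 days after the last dose, without a stated 24-hour limit.

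**The concern.** Two nearly identical paragraphs in the same chapter set different scopes for the same duty, and the design section sides with the narrower one. A site that takes its rule from 4.1 or 7.3.5 follows an explicit instruction with its own scope and clock, and would have no reason to look for a wider one.

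The events affected are foreseeable in this population. Serious signs and symptoms of progressive disease are SAEs under 7.3.1, and an investigator may reasonably judge them unrelated to sorafenib. Section 7.3.4 bases the relationship judgement on the information available when the case report form is completed, and no deadline is given for that form. The narrow wording therefore makes a 24-hour duty depend on a judgement that has no clock of its own. What is at stake is how soon the sponsor's safety function sees these events and can form its own view.

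**Working it through.** No arithmetic applies; the plan states no figure on this point. The check sets the current texts side by side.

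| Protocol section | What it governs | Events covered | Time limit stated |
|---|---|---|---|
| 4.1 | Report to sponsor drug safety | Treatment-related SAEs | 24 hours |
| 7.3.5 | Report and SAE form | Treatment-related SAEs, on the investigator's assessment | 24 hours |
| 7.4 | Report and SAE form | All SAEs | 24 hours |
| 7.3.1 | Instruction to report serious events as such | No relatedness qualifier | None |
| 4.3, 4.6.3 | SAE form for deaths | Deaths up to 30 days after last dose, any relationship | None |
| 4.6.2, 4.6.3 | CRF recording | All SAEs | None |
| 5.2 | Monitors' check of timely reporting | Names treatment-related SAEs | Not applicable |
| 4.7 | Monitors' general duty | Whole protocol | Not applicable |

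**Step 1: what each rule implies for the first report.**
- SAE judged related: 24 hours under 4.1, 7.3.5 and 7.4. No conflict.
- Non-fatal SAE judged unrelated: 24 hours under 7.4; no stated limit under 4.1 or 7.3.5.
- Fatal SAE judged unrelated: 24 hours under 7.4. Sections 4.3 and 4.6.3 ensure that a form is completed but set no 24-hour limit, so they do not settle its timing.

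**Step 2: is there a tie-breaker?** None is stated. The closest is the advice in 7.4 to consult the study monitor when in doubt. That gives the site someone to ask but does not name the governing rule, and it helps only a site that notices the conflict.

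**Step 3: do other sentences close the gap?** The closing sentence of 7.3.5 requires updated reports for each SAE but sets no clock for the first one. CRF capture is complete in scope but has no stated deadline.

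**Step 4: does the analysis change?** No. SAP 6.4 tabulates both all and drug-related treatment-emergent SAEs, and both rest on CRF data that must contain every SAE.

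**Separate check: follow-up of AEs leading to discontinuation.** Section 4.3 requires follow-up until recovery or stabilization. Section 4.6.3 stops at resolution, stabilization or 30 days, whichever comes first. SAEs are already followed to resolution or stabilization under 7.3.5 and 7.4. The conflict is therefore left with non-serious events or laboratory abnormalities that are neither resolved nor stable at day 30. Section 7.2 agrees with 4.3 but is weak support: the Amendment 3 overview (10.3.1, Modification 4) ties that added sentence to Japanese requirements, and 10.6.8 says that no patients remain on treatment at Japanese sites.

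**The case against.** The strongest reply is that the clauses are compatible. Sections 4.1 and 7.3.5 say that related SAEs must be reported in 24 hours; neither says that unrelated ones need not be. Section 7.4 carries reporting in its title, while 7.3.5 is headed as a section on severity. Section 7.3.1 supports the wider scope. So do the pregnancy rules in 4.3 and 7.4, which borrow the SAE timeline without qualification, as if there were one clock. On this view a site misses a report only by overlooking 7.4.

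That is right as far as it goes: the plan does contain a sufficient rule. But a restriction placed in front of one of two otherwise near-identical paragraphs invites the reading that it is meant, and the design section repeats it.

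A second reply is that the direction of the correction is assumed. Related-only expedited reporting may have been intended, with the unqualified 7.4 as the slip. The study file and the forms provided, which might settle this, are not among the documents. This stands as a reason for the sponsor to confirm the intended scope. It does not remove the conflict. In its absence the wider rule is the safer default, since it satisfies every section.

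A reader might also infer from 5.2 that monitors check timeliness for treatment-related SAEs and for no others. The documents do not support that. Section 5.2 names those events without saying that they are the only ones, and the general duty in 4.7 takes in 7.4.

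**Conclusion.** The inconsistency is real, sits in current text and should be corrected. Two sections setting the duty (4.1, 7.3.5) carry the qualifier, as does one sentence on monitoring (5.2). The dedicated reporting section (7.4) does not, and 7.3.1 leans the same way as 7.4.

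Its size is limited. For an SAE judged unrelated, the first report is due in 24 hours under one section and has no stated limit under two others. No delay in days can be derived, because the documents give no CRF timing, and the number of such SAEs is not given. The conclusion assumes that some sites work from 4.1 or 7.3.5 and have no separate instruction in the study file.

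Three stronger readings should be resisted.
- The SAP's safety tables are not put at risk, because CRF capture does not depend on attribution.
- Deaths are not exempt from the timing question. Their form route ensures notification, not notification within 24 hours.
- A claim of harm to the expectedness assessment would be thin. Section 7.3.3 says that expectedness will "be determined by the Sponsor according to the applicable reference document and according to all local regulations", but it defines unexpected events as adverse drug events. For an SAE judged unrelated, that matters mainly if the sponsor takes a different view of causality.

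The follow-up conflict between 4.3 and 4.6.3 is also real, but separate and minor.

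**What to change.** Delete *treatment related* from 4.1, 5.2 and 7.3.5, and *as assessed by the investigator* from 7.3.5, so that all three match 7.4. A lighter alternative is one sentence saying that 7.4 governs the scope and timing of SAE reporting and that the monitoring in 5.2 covers all SAEs. The sponsor should confirm the intended scope when doing so.

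The vehicle can be an administrative letter or the next amendment. There is precedent: the sponsor used a letter and then an amendment when 4.5.8 disagreed with the exclusion criteria on TACE (10.4.1, Modification 5). The downside is a modest increase in expedited reports at sites that used the narrower scope.

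For the minor point, align 4.6.3 with 4.3 by removing the 30-day cap on AEs leading to discontinuation. The general 30-day follow-up statement in 4.6.3 and footnote d of the flow chart (11.1) then need an exception for events that must be followed to recovery or stabilization. This means some event follow-up beyond day 30, which works slightly against Amendment 7's aim of reducing burden and letting sites close. It does not bring back survival follow-up.
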